1.0 TRIAL SUMMARY

Abbreviated Title	Pilot study of pembrolizumab treatment for disease relapse after allogeneic stem cell transplantation
Trial Phase	Pilot study
Clinical Indication	Classical Hodgkin lymphoma (cHL), B cell non-Hodgkin lymphoma (B-NHL), acute myeloid leukemia (AML), myelodysplastic syndromes (MDS)
Trial Type	Interventional
Type of control	None
Route of administration	Intravenous
Trial Blinding	None
Treatment Groups	1
Number of trial subjects	12-26
Estimated enrollment period	10-20 months
Estimated duration of trial	36-48 months
Duration of Participation	35 cycles (up to 2 years)

2.0 TRIAL DESIGN

2.1 TRIAL DESIGN

This pilot study has been designed to investigate the safety of pembrolizumab treatment for disease relapse following allogeneic stem cell transplant (alloSCT). Pembrolizumab will be administered at a fixed dose of 200 mg IV every 3 weeks. Approximately 12-26 patients with relapsed MDS, AML, or mature B cell (B-NHL, cHL) malignancies that

have relapsed following alloSCT will be enrolled on this trial. Pembrolizumab treatment will be administered for up to 24 months, provided that neither disease progression, nor development of a dose-limiting toxicity (DLT), has occurred. Adverse events will be monitored every three weeks throughout the trial and graded in severity according to the guidelines outlined in the NCI Common Terminology Criteria for Adverse Events (CTCAE) version 4.0. This trial will be conducted in accordance with Good Clinical Practices.

Briefly, patients will undergo baseline eligibility screening within 2 weeks prior to enrollment, including a medical history, physical examination, and assessment of performance status and hematology and chemistry parameters. Baseline assessment of disease status will be based on results of a bone marrow aspirate and biopsy for patients with AML and MDS, and a CT/PET scan (with a bone marrow exam for history of disease involvement) for patients with lymphoma. Baseline and subsequent bone marrow and peripheral blood samples will be obtained for correlative assays. Disease response assessment (bone marrow aspirate and biopsy and/or CT/PET) will be performed at baseline, and then every 3 months for 2 years, as well as any time if relapse is suspected. Specific procedures to be performed during the trial, as well as their prescribed times and associated visit windows, are outlined in the trial flow chart – Section 7.0. Details of each procedure are provided in Section 8.0 – trial procedures. After 24 months, ongoing disease re-assessments will be performed at the discretion of the treating physician. Any patient who experiences biopsy-proven disease progression at any time will be removed from study, and alternative treatment can be recommended at the treating physician's discretion. Subjects are not eligible for re-treatment on with pembrolizumab in the setting of this protocol should they experience a disease relapse after completing 24 months of therapy. After the end of treatment, each subject will be followed for 30 days for adverse event monitoring (serious adverse events will be collected for 90 days after the end of treatment). Subjects who discontinue treatment for reasons other than disease progression will have post-treatment follow-up for disease status until disease progression, initiating a non-study cancer treatment, withdrawal of consent, or becoming lost to follow-up. All subjects will be followed by telephone contact for overall survival until death, withdrawal of consent or the end of the study, whichever comes first.

The primary objective of this trial is to determine whether administration of pembrolizumab is tolerable in patients who have experienced disease relapse following alloSCT. Secondary objectives include analysis of efficacy parameters (ORR, DOR, OS). Correlative studies to examine the effect of PD-1 blockade therapy on T cell parameters and clonality, as well as on donor chimerism are planned as exploratory analyses.

A DLT is defined as the development of grade 3 or 4 acute GVHD (defined by the Gluckensberg scale), graft rejection, the development of any unexpected grade > 2 toxicity felt to be related to pembrolizumab, or the development of > grade 2 dysfunction of a vital organ felt to be secondary to an immune-related adverse event within 90 days following the initiation of pembrolizumab treatment. For immune-related adverse events that do not meet criteria for a DLT, but do meet criteria for a treatment-limiting toxicity (TLT), for example grade 2 acute GVHD, pembrolizumab will be held until the toxicity has

decreased to \leq grade 1. It will be permanently discontinued if delayed for >12 weeks. For patients who develop GVHD or an immune-related adverse event while on pembrolizumab, corticosteroid therapy and potentially other immunomodulatory agents will be initiated.

If the safety and feasibility of pembrolizumab is confirmed in this patient cohort, a phase II expansion cohort may be considered, particularly for disease subtypes where objective responses have been observed.

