Hyperthyroidism or Hypothyroidism	3 ¹	Toxicity resolves to Grade 0-1	Toxicity does not resolve within 12 weeks of last dose or inability to reduce corticosteroid to 10 mg or less of prednisone or equivalent per day within 12 weeks.
	4 ¹	Permanently	Permanently discontinue

Toxicity	Hold Treatment For Grade	Timing for Restarting Treatment	Discontinue Subject
		discontinue	
Infusion Reaction	3-4	Permanently discontinue	Permanently discontinue
Neurologic events (including myasthenia gravis)	2 ¹	Toxicity resolves to Grade 0-1. Re-start pembrolizumab at 200 mg IV q21 days.	Toxicity does not resolve within 12 weeks of last dose or inability to reduce corticosteroid to 10 mg or less of prednisone or equivalent per day within 12 weeks.
	3-4 ¹	Permanently discontinue	Permanently discontinue
Pneumonitis	2 ¹	Toxicity resolves to Grade 0-1. Re-start pembrolizumab at 200 mg IV q21 days.	Toxicity does not resolve within 12 weeks of last dose or inability to reduce corticosteroid to 10 mg or less of prednisone or equivalent per day within 12 weeks.
	3-4 ¹	Permanently discontinue	Permanently discontinue
Renal Failure or Nephritis	2 ¹	Toxicity resolves to Grade 0-1. Re-start pembrolizumab at 200 mg IV q21 days.	Toxicity does not resolve within 12 weeks of last dose or inability to reduce corticosteroid to 10 mg or less of prednisone or equivalent per day within 12 weeks.
	3-4 ¹	Permanently discontinue	Permanently discontinue
All Other Drug-Related Toxicity ³	3 Severe ¹ or	Toxicity resolves to Grade 0-1. Re-start pembrolizumab at 200 mg IV q21 days.	Toxicity does not resolve within 12 weeks of last dose or inability to reduce corticosteroid to 10 mg or less of prednisone or equivalent per day within 12 weeks.

Toxicity	Hold Treatment For Grade	Timing for Restarting Treatment	Discontinue Subject
	4	Permanently discontinue	Permanently discontinue

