6.6 RESCUE MEDICATIONS AND SUPPORTIVE CARE

6.6.1 SUPPORTIVE CARE GUIDELINES

Subjects should receive appropriate supportive care measures as deemed necessary by the treating physician, including but not limited to the items outlined below:

- Diarrhea: Subjects should be carefully monitored for signs and symptoms of enterocolitis (such as diarrhea, abdominal pain, blood or mucus in stool, with or without fever) and bowel perforation (such as peritoneal signs and ileus). Diarrhea in this particular patient population may be due either to acute GVHD or to classical pembrolizumab-induced enterocolitis, and the differentiation between the two may be difficult or impossible. In symptomatic subjects, infectious etiologies should be evaluated, and if symptoms are persistent and/or severe, endoscopic evaluation should be performed.
- In subjects with severe enterocolitis (grade 3 or 4) caused by acute GVHD or classical pembrolizumab-associated enterocolitis, pembrolizumab will be permanently discontinued, and treatment with systemic corticosteroids should be initiated at a dose of 1-2 mg/kg/day of prednisone or equivalent. When symptoms improve to \leq grade 1, a corticosteroid taper should be started and continued for > 1 month.
- In subjects with moderate enterocolitis (grade 2) caused by acute GVHD or classical pembrolizumab-associated enterocolitis, pembrolizumab will be withheld and corticosteroids should be initiated at a dose of 1 mg/kg/day of prednisone or equivalent. When symptoms improve to \leq grade 1, a corticosteroid taper should be started and continued for > 1 month. Pembrolizumab may be re-started at 200 mg IV every 21 days, as outlined in Section 6.2.1.2.
- All subjects who experience diarrhea should be advised to drink liberal quantities of clear fluids. If sufficient oral fluid intake is not feasible, fluid and electrolyte repletion (IV) is appropriate. Other treatments, including loperamide, oral non-absorbable corticosteroids and octreotide may be administered according to institutional guidelines for the treatment of acute GVHD.
- GVHD: Subjects should be carefully monitored for signs and symptoms of GVHD (including diarrhea, transaminitis, rash). These symptoms will be treated aggressively with topical and/or systemic steroids and additional immunosuppressants per institutional guidelines.

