9.2.4 STATISTICAL METHODS

9.2.4.1 STATISTICAL METHODS FOR TOLERABILITY ANALYSES

The trial will feature a two-stage minimax trial design (Simon 1989, A'hern, 2001) which tests for futility in a smaller sample of patients before proceeding with treatment of the full cohort. The accrual rate will be 1 patient/month in relapsed/refractory myeloid and B cell malignancies following allogeneic stem cell transplant to assess the safety and feasibility of pembrolizumab. The primary outcome is whether the patient remains DLT-free at the end of treatment. *A priori*, we expect 40% or fewer patients on an unsafe treatment would finish without experiencing a DLT, and at least 65% of patients would be DLT-free on a safe treatment. For $\alpha = 0.05$ and 80% power, we would need to observe

at least 5 DLT-free treatments out of a small sub-sample of 12 patients before we would consider evaluating pembrolizumab in the full sample of 26 patients. If at least 14 of the 26 patients respond remain DLT-free, we would have sufficient evidence to warrant further study of pembrolizumab in a future trial.

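### Severe enterocolitis is a DLT if called acute GVHD but only conditionally so if called pembrolizumab colitis, and the protocol doubts the two can be separated, so a toxicity stop can count as DLT-free

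*Combined protocol and SAP*

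**What the plan says.** **DLT definition (2.1).** The first limb carries no condition on expectedness or organ: "A DLT is defined as the development of grade 3 or 4 acute GVHD (defined by the Gluckensberg scale), graft rejection". The second is "the development of any unexpected grade > 2 toxicity felt to be related to pembrolizumab". The third is, above grade 2, "dysfunction of a vital organ felt to be secondary to an immune-related adverse event". The section sets a 90-day window from the start of treatment. It does not say which toxicities are expected or which organs are vital.

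**Enterocolitis (6.6.1).** Diarrhea may come from acute GVHD or from the drug's own enterocolitis, and "the differentiation between the two may be difficult or impossible". Grade 3 or 4 cases are handled alike: when "caused by acute GVHD or classical pembrolizumab-associated enterocolitis, pembrolizumab will be permanently discontinued".

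**Dose modification (6.2.1.2, Table 5).** Diarrhea/colitis has its own row, with permanent discontinuation at grade 3-4. Grade 3-4 infusion reactions, grade 3-4 neurologic events and grade 4 thyroid events also end treatment permanently.

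**Primary outcome (9.2.4.1).** "The primary outcome is whether the patient remains DLT-free at the end of treatment". The trial goes to 26 patients if at least 5 of 12 are DLT-free, and the drug merits further study if at least 14 of 26 are. Sections 9.1.1 and 9.1.3 also halt the trial if 5 or more of the first 12 patients have a DLT.

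**The concern.** The primary outcome is meant to measure tolerability, and the hypothesis in 3.1 covers immune-related events generally, with GVHD as one of them. A patient taken off the drug for good because of severe drug-related enterocolitis has not tolerated it. Under 2.1 that patient is certainly a DLT if the investigator writes acute GVHD. If the investigator writes pembrolizumab colitis, the answer depends on two undefined words.

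The trial is open-label, and attribution is left to the investigator under Table 5. No adjudication of the label is described: the independent review in 12.6.6 covers response and progression only. The rule closing accrual after severe GVHD in each of the first five patients depends on the same label. The endpoint can therefore lean toward 'tolerable', and two assessors can score the same patient differently.

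**Working it through.** **Step 1. The same event under two labels.** Take a grade 3-4 enterocolitis within the 90-day window that the investigator judges drug-related.

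| | Labelled acute GVHD | Labelled pembrolizumab colitis |
|---|---|---|
| Treatment (6.6.1, Table 5) | Permanent stop | Permanent stop |
| DLT (2.1) | Yes, if grade 3-4 on the GVHD scale | Only if 'unexpected' or 'vital organ' dysfunction |
| Is it 'unexpected'? | Not asked | Not defined; 6.6.1 calls this form classical |
| Is bowel a 'vital organ'? | Not asked | Not stated |
| Final count (14 of 26) | Failure | Failure or success, by judgement |

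GVHD is graded on its own scale (12.6.7) and other events by CTCAE. Section 6.6.1 does not say which scale its grade 3 or 4 uses, so the grade may change with the label too.

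**Step 2. Can a stopped patient still be a success?** Sections 8.2 and 9.1.1 require the first-stage patients to complete treatment without a DLT, which may exclude a stopped patient at that stage. Section 9.1.3 counts DLTs only. Section 9.2.4.1 speaks of finishing without a DLT when it sets the 40% rate, but its final rule asks only that patients remain DLT-free. The final decision therefore does not clearly exclude a stopped patient.

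**Step 3. The plan's own figures.** Inputs from 9.2.4.1 are p0 = 0.40, p1 = 0.65, alpha 0.05 and power 0.80, with 12 then 26 patients. For cut-offs c (of 12) and a (of 26),

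P(pass | p) = sum over x = c to 12 of Bin(x; 12, p) × P[Bin(14, p) ≥ a − x].

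- Printed cut-offs (c = 5, a = 14): 0.104 at p0 and 0.907 at p1. The stated alpha and power do not reproduce.
- Minimax search for the stated inputs: the sizes 12 and 26 reproduce, with c = 6 and a = 15, alpha 0.047 and power 0.809.
- Halt at 5 or more DLTs applied at the first stage (c = 8, a = 14): 0.033 at p0 and 0.576 at p1.

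The cut-off discrepancy is a separate matter. All three rules are carried forward because it affects the baseline.

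**Step 4. Effect of uncounted events.** Let m be the share of all patients permanently stopped for such toxicity but scored DLT-free. The documents give no value, so m = 5 and 10 points are assumptions. If the true failure-free rate is 0.40, the measured rate is 0.40 + m.

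| Rule | m = 0 (0.40) | m = 5 points (0.45) | m = 10 points (0.50) |
|---|---|---|---|
| Printed, ≥5/12 then ≥14/26 | 0.104 | 0.230 | 0.410 |
| Minimax, ≥6/12 then ≥15/26 | 0.047 | 0.123 | 0.257 |
| With halt at ≥5 DLTs, ≥8/12 then ≥14/26 | 0.033 | 0.081 | 0.163 |

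In patients, 0.05 × 26 = 1.3 and 0.10 × 26 = 2.6. A single patient is 1/26 = 3.8% of the final sample.

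**The case against.** **Context narrows the gap.** Table 1 has two tiers, one that holds treatment and may restart it and one (DLT) that discontinues it, and a Table 5 footnote refers to DLT-grade toxicity. On that reading the permanent-stop grades in Table 5 are the DLT grades. An investigator could also class severe colitis as vital-organ dysfunction. Both readings are fair, but 2.1 states neither, so they show that the text allows more than one answer.

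**A Table 5 row does not prove an event is expected.** The table ends with a row for all other drug-related toxicity, so that test would leave nothing unexpected. This stands. The better evidence is the word 'classical' in 6.6.1, and that suggests rather than settles the matter.

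**The completion wording may already catch these patients.** It may at the first stage, but not clearly in 9.1.3 or in the final rule.

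**The events are not hidden.** Section 5.3 requires adverse events to be analysed and Table 11 records whether an event led to discontinuation. That is true, but the go/no-go decision uses only the DLT-free count.

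**Redefining DLT would reach beyond the endpoint.** Under Table 1 a DLT removes the patient from study, whereas 6.8 and 8.1.6.1 keep patients who stop treatment under observation. DLT counts also close accrual, and the 40% and 65% rates are stated for DLT-free status. A reader might infer that every permanent-stop event in Table 5 should become a DLT and that this is mere wording. The documents do not support that: it would alter who is removed and when the trial halts, and would test a broader endpoint against benchmarks set for a narrower one.

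**Conclusion.** The point holds as a gap in the endpoint definition. For severe enterocolitis, the primary outcome can turn on an unblinded label that the protocol itself doubts, and a patient permanently stopped for drug-related toxicity can count as DLT-free in the 14-of-26 decision. Other permanent-stop events in Table 5, such as grade 3-4 infusion reactions, have the same uncertain status.

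A reader might infer that such patients will be scored as successes, or that the result is biased by a known amount. Neither follows. The text permits the favourable scoring without requiring it, and the size rests on an assumed 5 or 10 points of missed events. The printed-rule result (0.104 rising to 0.230 or 0.410) is the least favourable of the three rules checked. With the halt rule applied, the pass probability at 10 points is 0.163. Under every rule checked, missing 5 points at least doubles the chance of passing a treatment at the protocol's own unsafe limit. The change should be made, though the point does not invalidate the design.

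**What to change.** 1. In 2.1 and 9.2.4.1, for the primary DLT-free endpoint, count grade 3-4 enterocolitis as a failure whether it is attributed to acute GVHD or to pembrolizumab. Name the grading scale, and report the attribution only as a descriptive breakdown.
2. Add to 9.2.4.1 a prespecified sensitivity analysis of the DLT-free proportion that counts every permanent discontinuation for pembrolizumab-related toxicity as a failure. This covers the other Table 5 events without redefining them all as DLTs.
3. Reconcile 2.1, Table 1 (a DLT means removal from study), Table 5, and 6.8 with 8.1.6.1 (follow-up continues after treatment stops). Which clinical rule applies is for the sponsor to decide. The sponsor should also confirm that the 40% and 65% rates and the halt at 5 or more DLTs fit the clarified endpoint.

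Cost: no new data, since grade, attribution and discontinuation are already recorded. The work is a protocol amendment, one added analysis and a check of the design rates. The DLT-free proportion may come out slightly lower, and more events may count toward the halt rule.

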2.2 TRIAL OVERVIEW

The trial overview is depicted in **Table 1**.

Table 1. Trial overview

Initial treatment	Pembrolizumab 200 mg IV on day 1 of each 21 day cycle
Treatment-limiting toxicity (TLT) (for example, grade 2 acute GVHD)	Hold treatment for up to 12 weeks.. For immune-related adverse events that do not meet criteria for a DLT, but do meet criteria for a treatment-limiting toxicity (TLT), for example grade 2 acute GVHD, pembrolizumab can be restarted provided that the toxicity has decreased to $<$ grade 2. For patients who develop GVHD or an immune-related adverse event while on pembrolizumab, corticosteroid therapy and potentially other immunomodulatory agents will be initiated. Re-start treatment with pembrolizumab 200 mg IV on day 1 of each 21 day cycle, provided that the TLT has resolved to \leq grade 1. Permanently discontinue if no improvement in toxicity to \leq grade 1 in 12 weeks.
Dose-limiting toxicity (DLT)	Discontinue treatment. Remove patient from study

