
Note: Permanently discontinue for any severe or Grade 3 drug-related AE that recurs or any life-threatening event.
 
¹ Administer corticosteroid (See also Events of Clinical Interest Guidance Document and Section 8.2.3.2 Events of Clinical Interest).
 
² For patients with liver metastasis who begin treatment with Grade 2 AST or ALT, if AST or ALT increases by greater than or equal to 50% relative to baseline and lasts for at least 1 week then patients should be discontinued.
 
³ Patients with intolerable or persistent Grade 2 drug-related AE may hold study medication at physician discretion. Permanently discontinue study drug for persistent Grade 2 adverse reactions for which treatment with study drug has been held, that do not recover to Grade 0-1 within 12 weeks of the last dose.
 
* Attribution of events to drug will be per investigator/physician discretion; in case of DLT grade toxicity that is deemed to be unrelated to drug, patient can continue on trial with appropriate treatment
			

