6.8 SUBJECT WITHDRAWAL/DISCONTINUATION CRITERIA

Subjects may withdraw consent at any time for any reason or be removed from the trial at the discretion of the investigator should any untoward effect occur. In addition, a subject may be withdrawn by the investigator or the sponsor if enrollment into the trial is inappropriate, the trial plan is violated, or for administrative and/or other safety reasons.

A subject must be discontinued from the trial for any of the following reasons:

- The subject or legal representative (such as a parent or legal guardian) withdraws consent.

A subject must be discontinued from treatment (but may continue to be monitored in the trial) for any of the following reasons:

- The subject or legal representative withdraws consent for treatment
- Disease progression occurs
- Unacceptable AEs develop as described in Tables 5 and 6, and Sections 6.6.1.1 and 6.6.1.2
- Intercurrent illness develops that prevents further administration of pembrolizumab
- Investigator's decision
- The subject becomes pregnant
- The subject is non-compliant with the treatment or trial requirements

- The subject is lost to follow-up
- Administrative reasons

The end of treatment and follow-up visit procedures are listed in Section 7.0 (Trial flow chart) and Section 8.1.5 (Visit Requirements). After the end of treatment, each subject will be followed for 30 days for adverse event monitoring (serious adverse events will be collected for 90 days after the end of treatment). Subjects who discontinue for reasons other than progressive disease will have post-treatment follow-up for disease status until disease progression, initiating a non-study cancer treatment, withdrawing consent or becoming lost to follow-up. After documented disease progression or the start of new anti-cancer therapy, each subject will be followed by telephone for overall survival until death, withdrawal of consent, or the end of the study, whichever occurs first.

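### Table 5 lets a patient restart after an unexpected, related grade 3 event that Section 2.1 and Table 1 treat as a treatment-ending DLT, and its grade 4 hypophysitis row contradicts the table's own note

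*Combined protocol and SAP*

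**What the plan says.** **DLT rule.** Section 2.1 lists four kinds of DLT. One is "the development of any unexpected grade > 2 toxicity felt to be related to pembrolizumab". The list closes with a window of 90 days from the start of pembrolizumab. The same section allows treatment for up to 24 months "provided that neither disease progression, nor development of a dose-limiting toxicity (DLT), has occurred". Table 1 (Section 2.2) gives the action for a DLT: "Discontinue treatment. Remove patient from study". Both places describe hold-and-restart for immune-related events that fall short of a DLT.

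**Dosing table.** Table 5 (Section 6.2.1.2) sets the action by toxicity and grade. Its last row, "All Other Drug-Related Toxicity", covers anything without its own row. At grade 3 or severe, drug is held until grade 0-1, and then the instruction is "Re-start pembrolizumab at 200 mg IV q21 days". At grade 4, drug stops for good. The note beneath reads: "Permanently discontinue for any severe or Grade 3 drug-related AE that recurs or any life-threatening event". A further footnote says that "in case of DLT grade toxicity that is deemed to be unrelated to drug, patient can continue on trial with appropriate treatment".

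**Hypophysitis.** At grade 4, the restart-timing column of Table 5 gives resolution to grade 0-1. The patient is discontinued only if the event has not resolved, or steroids cannot be reduced to 10 mg or less of prednisone equivalent per day, within 12 weeks.

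**Stopping list.** Section 6.8 lists the reasons for which treatment must stop. A DLT is not among them. The toxicity entry is "Unacceptable AEs develop as described in Tables 5 and 6, and Sections 6.6.1.1 and 6.6.1.2".

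**The concern.** The same event draws opposite instructions depending on which section the treating physician opens. An unexpected, severe, drug-related toxicity soon after the start of treatment is one that Section 2.1 regards as ending therapy. A physician working from the dosing table and the stopping list would instead restart at the full 200 mg once the event settled. For grade 4 hypophysitis the disagreement lies within a single table.

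The stakes are patient safety and consistent conduct. Tolerability is the primary objective, and Section 4.3 says that PD-1 blockade had not been formally tested in people after transplant. Two investigators could manage identical patients differently. No miscount of the primary outcome is alleged: a DLT is defined by the event, so it can be counted whatever was done with the dose.

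**Working it through.** The plan states no figure to reproduce here. The check compares the texts and counts the rows of Table 5.

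**Step 1: follow one event through the protocol.** Take a grade 3 toxicity that is related, unexpected, within 90 days, and without a row of its own in Table 5.

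| Place | Instruction for this event |
|---|---|
| 2.1, DLT definition | It is a DLT (grade 3 is above grade 2) |
| 2.1, condition for treatment | No further drug after a DLT |
| Table 1 | Stop treatment, leave the study |
| Table 5, last row, grade 3 | Hold, then restart at 200 mg once grade 0-1 |
| Table 5 note | Permanent stop only if the grade 3 or severe event recurs, or is life-threatening |
| 6.2.2 | Restart after recovery from a treatment-limiting toxicity (TLT), which it defines by 6.2.1.2 and Table 5 |
| 6.8 | No DLT entry; refers to Tables 5 and 6 and Sections 6.6.1.1 and 6.6.1.2 |
| 8.2.4, Table 11 | Some rechallenges need the principal investigator's prior approval, under the dose modification guidelines, which leads back to Table 5 |

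The first three lines end treatment. Table 5 restarts it, and the remaining lines either support the restart or refer back to Table 5. Neither the Table 5 row nor its note excludes DLTs, unexpected events or the first 90 days.

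**Step 2: grade 4 hypophysitis.** The row gives a restart condition. The note requires a permanent stop for any life-threatening event. Table 11 describes CTCAE grade 4 as having life-threatening consequences. By the note the patient stops; by the row the patient may restart.

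**Step 3: count the rows of Table 5.**

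| Category | Grade 3 | Grade 4 |
|---|---|---|
| Acute GVHD | stop | stop |
| Diarrhea/colitis | stop | stop |
| Hypophysitis | restart | **restart** |
| AST, ALT or bilirubin | stop (footnoted exception) | stop (footnoted exception) |
| Thyroid | restart | stop |
| Infusion reaction | stop | stop |
| Neurologic | stop | stop |
| Pneumonitis | stop | stop |
| Renal | stop | stop |
| All other | **restart** | stop |

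- Grade 3: 7 of 10 stop; 10 − 7 = 3 allow restart (hypophysitis, thyroid, all other).
- Grade 4: 9 of 10 stop; 10 − 9 = 1 allows restart (hypophysitis).

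The two cells in bold are the subject of this point. The first is in conflict only for unexpected, related events inside the 90-day window. For expected events, or later ones, the row can stand.

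**A related gap.** Table 4 does not hold drug for related hematological toxicity of grade 1 to 3, yet an unexpected, related grade 3 event of that kind would also be a DLT under Section 2.1.

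**The case against.** The strongest reply is that the documents already imply which rule prevails. Section 2.1 and Table 1 describe hold-and-restart for events that are not DLTs. Section 6.2.2 presents the Table 5 restart as the path for a TLT. The Table 5 footnote lets patients with DLT-grade toxicity continue when the event is unrelated to drug, which suggests that related ones do not. Section 6.2.2 also requires the two investigators to consult and document interruptions of more than 3 days and up to 3 weeks, so a restart would often not be one physician's decision. On this view Part 1 is a missing clarification.

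Part of this stands: a careful reader can infer that the DLT rule comes first. The inference does not change what the row says, and nothing in Table 5 points the reader to Section 2.1. Section 6.2.2 makes matters worse, because it defines a TLT by reference to 6.2.1.2 and Table 5, which puts this event on the restart path. The consultation requirement says who talks to whom but not what they should decide, and Table 5 is the guidance they would consult. In 6.8, the investigator's discretion allows a stop but does not require one.

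A second objection is that the 90-day window may attach only to the last kind of DLT listed in Section 2.1. If so, the overlap is larger, not smaller. The narrower reading is used here, and it fits Section 9.1.1, which ties severe GVHD as a DLT to the first 90 days.

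On hypophysitis, one can say that the row and note read together favor stopping, and that a guidance document not included here may cover the case. Neither removes the disagreement within the table.

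**Conclusion.** Both contradictions hold as stated and should be fixed. For an unexpected, related grade 3 event within 90 days and without its own row, Table 5 instructs a restart that Section 2.1 and Table 1 forbid. For grade 4 hypophysitis, Table 5's row permits a restart that its own note forbids.

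The extent is two rows of one table. How many patients would be affected cannot be derived, because the documents give no rate for either event; the number is zero if investigators already give priority to Section 2.1 and to the note. The conclusion assumes that Section 2.1 and Table 1 express the intended rule for DLTs. For hypophysitis the intention is unknown. The sample size, the stopping rules and the DLT count do not depend on this point.

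**What to change.** 1. In 6.2.1.2, add a sentence stating that hold-and-restart applies only to events that do not meet the Section 2.1 DLT definition, and that any event meeting it is managed per Table 1. Placed ahead of Tables 4 and 5, it also closes the Table 4 gap.
2. In the 6.8 list of reasons to stop treatment, add the occurrence of a DLT as defined in Section 2.1.
3. Make the grade 4 hypophysitis row agree with the note: either change it to permanent discontinuation, as in the other 9 categories, or, if restart is intended, name it in the note as an exception.

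The cost is one sentence, one bullet, and one table cell or one phrase in the note. Sample size, endpoints and visits stay as they are. A few patients might stop drug who could otherwise have restarted, but Section 2.1, Table 1 and the note already require them to stop.
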